### *III g Electronic Diaries during Sampling*

All participants will be asked to complete a brief diary to assess smoking behavior and use of meds. These diaries, which will include brief mood assessments, provide additional, real-time risk monitoring, not to replace traditional adverse event assessment (above), but to complement. Our intent is to better capture day-to-day fluctuations in medication use and smoking. Each of our recent trials have used this diary approach, with excellent compliance (88% for one study, 83% for another). Diaries will assess cigarettes smoked per day, medications/products used, purposes of that use (to reduce/quit), and mood/affect. Diaries ( $\leq 2$  min each) will be electronically collected daily throughout the sampling period (28 days). We have established procedures to auto-send an email/text on a set schedule. Thus, per eligibility criteria above, we require participants to have smartphone capacity, and they will be compensated for compliance based on % diaries completed (e.g., \$100 for 90-100% compliance, \$70 for 75-90% compliance, etc.). There is some debate as to whether EMA/diary procedures alter behavior, but recent evidence suggests not,(95, 96) but even if so this is equal between groups.

### *IIIh Remote CO Collection*

Our prior remote trials did not include biological verification of smoking. With minimal intensity 'interventions' we view the bias of demand characteristics as low. However, we recognize that biological verification is certainly a strength. MUSC investigators are on the forefront of real-time remote CO collection (K23 DA045766, R34 DA042228, forthcoming NCI R21), in which all participants are provided an iCO Smokerlyzer at the time of enrollment. The device connects to a smartphone (both Android and iOS); thus, we require this as an eligibility criterion. The iCO can detect CO concentrations of 0-100 ppm, and has strong test-retest reliability, as well as concordance with traditional device.(97) Each follow-up will include instructions to complete the iCO breathalyzer, plugging it into their phone to capture video confirmation and all CO readings (time/date stamped). Thus, the procedure provides objective recordings. As of this writing, our group is working on methods to eliminate the need for an app altogether, instead interfacing with REDCap directly (secure, online, real-time data capture); [name] has ACS and forthcoming R21 funding explicitly for this purpose. The \$70 iCO device can be used repeatedly within a person, but it is not returned at end of study as it is not transferable to another user. A portion of participant compensation is contingent upon iCO compliance (not abstinence). We do not envision iCO testing within each daily diary, but we will add it for any reports of non-smoking, offering an additional method to corroborate quit attempts in real-time, heretofore not possible. These procedures have worked well in pilot testing, but we recognize that they are far from well-established. Alternative options are less feasible. First, we could mail a more established device (piCO), have the person return it after use, and transfer it to another participant. We have investigators at MUSC who are doing so with success. Ostensibly, however, this is no different than above, and allows fewer participants in the trial at one time (infeasible to purchase one device per participant). So, this is not our preferred method. Second, we could send at-home saliva collection kits, and have them returned to our lab for cotinine testing. These methods are more established, yet still unsatisfactory, in terms of compliance, biased responding, timeliness (asynchronized with survey responding), confounds of nicotine (NRT), and cost of assay. In the end, the iCO procedures are imperfect but still the best option available. We define abstinence as 7-day point prevalence (no smoking in prior week), with CO  $\leq$ 4ppm.(98, 99)

### *IIIi Power Estimations and Data Analyses*

Power: Our three-fold focus on outcomes includes 1) uptake (usage, conversion), 2) consequences (quit attempts, abstinence), and 3) mechanisms of varenicline and NRT sampling. We power on the most stringent of these to determine sample size: point-prevalence abstinence at six months (Aim 2), and we do so based on primary comparison of varenicline vs. inactive (non-sampling) control; see rationale above. Based on our early work, and under our belief that varenicline sampling will result in marginally better outcomes than NRT (12-15% in our prior studies) we anticipate a quit rate of 18% in varenicline vs. 8% in control, the latter also in line with our prior studies. With 2:1 randomization for this comparison (VRN:control), and with power of 80%, this will require a total sample size of 413 participants across these two groups. We conservatively inflate this by 15% to account for potential attrition, though in past studies this was closer to 12%, thus resulting in 324 varenicline vs. 162 control participants. We secondarily add another, active comparator group of smokers receiving NRT sampling (n=162; 2:1:1 overall randomization), for a **total of 648 participants**. If we were to power on varenicline vs. NRT outcomes, this would require a total sample of 1300 VRN + 650 NRT (+ 160 possible control), and such a study would be infeasible within this mechanism, and likely infeasible within any R01, particularly given the costs of medication. With anticipated 324 varenicline vs. 162 NRT participants, we have 39% power to detect a difference of 18% vs. 12% in abstinence. We have been doing studies this large for some time and have great confidence in recruitment. Over a 48-month recruitment span (see Timeline below), we aim to recruit ~11/month. For our ongoing nationwide trial of e-cigarettes (eventual N=660), we've averaged ~25/month. Considering the recruitment process and minor time delays between consent and formal enrollment, it is difficult to stop at an exact number. Thus, we will enroll between 648-660 participants to abide by those at earlier steps of the process.

Outcomes pertaining to uptake, usage and conversion (independent use of varenicline, NRT; Aim 1) are focused *within* each active treatment group individually, though we can compare each of these outcomes *between* medication groups as well, per binary/continuous analyses below. With 360 total participants in varenicline group, a two-sided 95% confidence interval will have a maximum half-width of 0.052 (e.g., 95% CI on an observed rate of 50% would range from 0.448 to 0.552). With 162 participants in NRT group, the maximum half-width for uptake parameters is .077. As the observed proportion deviates from 50% (either higher or lower), the 95% confidence interval will decrease in width, providing more precision on the estimate (e.g., 95% CI on 90% would range from 0.896 to 0.931 with n=324). A confidence interval as wide as +/- 5% is a relatively small width and one we are willing to accept for our estimates on uptake, and conversion. Formal mediation analyses (Aim 3: mechanisms of change, within and between groups) are not planned, but we can test whether the sampling intervention results

in greater change in mechanism variables (\*above) similarly vs. differently for varenicline vs. NRT. All analyses are based on an intent-to-treat approach and are nearly identical to analyses from our current and prior studies. Exploratory analysis will be performed on all variables to determine if transformations are needed. Any significant baseline differences between groups will be included in analyses. All analyses will be run separately for full intent-to-treat sample and those retained per protocol. We are specifically interested in whether sampling effects generalize to those who are and are not motivated to quit, and we will examine this via sensitivity (subgroup) analyses. We are under-powered for tests of treatment interactions.

Missing Data & Dropout: The most conservative approach for handling missing data(100) is to substitute them with baseline values, assuming outcomes have all returned to baseline, with no quit attempts made or abstinence achieved. If this assumption is incorrect, it biases the results towards the null by reducing between group differences.(100) We expect few missing data and thus plan for this approach. If missing data >10%, we will calculate results using this conservative method but also using methods in which missing data are imputed as described in the SRNT guidelines, and will assess whether dropout differs by study group (not the case in our prior trials). Abstinence will be reported both with and without (missing samples) CO verification.

Feasibility and Measures of Uptake: Our ongoing proof-of-concept study provides an early sense of study feasibility and thus this is not a main outcome of the trial. Nonetheless, we will deem our approach feasible if: a) at least 80% of varenicline group tries the medication, b) with reasonable duration of use (e.g., median days of use  $\geq 14$  days), c) at least 50% of varenicline group self-titrates to 2mg, d) at least 30% convert to independent use, and e) <5% of adverse events from varenicline are serious.

Binary Outcomes (incidence rate of quit attempts & cessation; % treatment uptake/conversion) will first be examined over the entire study period from baseline to end of follow-up by calculating frequencies/percentages as well as 95% confidence intervals for each medication group. Chi-square tests (or Fisher's exact tests as needed) will compare groups on binary outcomes to determine if effects from sampling group exceed those from control group. Both the control group (primary/powerful comparison) and NRT group (secondary) will serve as referent for varenicline group outcomes. Covariates will be included where necessary based on baseline differences. All tests will be considered significant at the  $\alpha=0.05$  level of significance.

Continuous Outcomes (duration of abstinence, smoking reduction) measured over the entire study period from baseline to the end of follow-up will be evaluated using general linear modeling with a main effect of group to determine group differences. Covariates will be added as necessary to account for baseline group differences.

Mechanisms of Change: We hypothesize that varenicline sampling will enhance quit motivation & confidence, as well knowledge of and attitudes toward medication, autonomy to quit, and will decrease cessation fatigue. We will examine all through analyses of continuous outcomes above. It will be interesting to explore whether and how these non-pharmacologic mechanisms differ for varenicline vs. NRT. Medication expectancies, knowledge, and familiarization might differentially vary through varenicline/NRT sampling, as might motivation and confidence. Note that our focus is on non-pharmacologic mechanisms, since the pharmacologic mechanisms of both varenicline and NRT are well-established and also since our design does not include a placebo comparator. Also note that formal tests of mediation can be explored but we may not be powered for these.

Diary Analyses: Mixed effects regression models(101) will be used to model diary data outcomes (e.g., days of med use) to allow for repeated observations per participant as well as for time-invariant (group, gender, etc.) and time-varying covariates (e.g., motivation to quit). These types of models allow for the inclusion of incomplete data across time, so we can include all reported data, even if <28 days per ppt. Any results obtained from these mixed effects models will be considered exploratory and primarily used to gather information on effect sizes.

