## II. Specific Aims

We propose a randomized clinical trial with **primary aims** to evaluate the: **1)** use, **2)** consequences (on cessation), and **3)** mechanisms of varenicline sampling. We will recruit between 648-660 smokers and randomize them to receive a 4-week sample of varenicline, NRT, or no sample, and will follow all for 6 months. Our remote focus derives from our hands-off (i.e., translatable) intent, yet our methods include both daily diary assessment and remote biological verification of smoking to enhance rigor. We are mindful of requirements for physician oversight and embed full precautions for safety. Our study sample will include smokers both wanting to quit and not (recruitment of each, with stratified randomization), which will allow for exploratory sensitivity analyses to assess the role of smoker motivation on outcomes.

In accordance with these Aims, we hypothesize that: 1) use of varenicline will be strong: >80% of study sample using medications on at least 50% of the sampling period; 2) relative to non-medication controls, sampling will result in higher incidence of quit attempts and biochemically verified cessation; 3) with greater changes in hypothesized mediators (motivation/confidence, decreases in treatment fatigue). Comparisons of varenicline vs NRT sampling a) uptake, b) mechanisms and c) outcomes are secondary but nonetheless compelling and offer additional significance, innovation, and rigor to our trial.

[figure not shown]

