### *IIIc Teleconsent, Baseline Assessment, & Randomization*

In our prior studies, recruitment from national sources was based on mail-based return of the consent form. That is, after determination of eligibility, we mailed a consent form (2 copies) and asked the participant to sign one copy and return to us in a pre-addressed, pre-stamped envelope. Receipt on our end is the start of official consent, and official enrollment begins with first phone call (Week 0). While this process generally worked, it was inefficient. For one, mailing delays often meant a lag between the person expressing interest and when s/he was officially enrolled. Second, there are occasional instances where the person does not fully complete the consent form (e.g., missing date), or does not return all necessary pages, and the process repeats itself (back and forth mailing) until we get all forms in full. Third, a large number (~55%) of the consent forms go un-returned, for any number of reasons. Thus, if we want a minimum of 648 participants, we would need to identify ~1180 who would be eligible and interested. Loss of interest in the study is a possibility (which we abide by), but we also believe that consents get lost, thrown away, regarded as junk mail (particularly if seen by someone else), etc. For the current study, we will continue with this procedure of mail-based consenting and add a new teleconsent process that addresses this inefficiency. After the initial determination of study eligibility, assessed online in our secure survey, participants will be asked about their capacity for teleconsent procedures, including access to a device and internet on which they can complete remote consent. For those who have the required hardware and software for teleconsent, we will then describe the basic mechanics of online consent process and ask for their preference for mode of consent: to be consented online or to receive a mailed consent. Participants can choose their preferred method of consent, and none of this is an eligibility requirement. Participants who do not meet teleconsent requirements will be mailed a consent form following standard procedures. Thus, we are simply offering another, more immediate option for study consent that may be preferable for some participants.

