**Figure of Study Flow for STARS**

Randomization, Stratification We recruit smokers wanting to quit ( $\geq 7$  on 0-10 scale) and not, and we use this as a stratification variable. We considered a number of other stratification variables (e.g. cigs/day, insurance status) but believe that randomization will adequately handle these. We will randomize participants to group in a 2:1:1 ratio, with intent to increase precision of our parameter estimates within the varenicline group (n=324), consistent with our intent to understand use patterns and uptake of varenicline.

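### Aim 1 precision is worked out for 360 varenicline participants where the plan gives 324 to 330, and the example interval at 90% is about half its correct width; separately, the stated recruitment pace falls short of 648

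*Combined protocol and SAP*

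**What the plan says.** All references are to the combined protocol and SAP.

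- Section IIIi, Aim 1 precision, gives the varenicline precision as "With 360 total participants in varenicline group, a two-sided 95% confidence interval will have a maximum half-width of 0.052", illustrated by an interval of 0.448 to 0.552 at an observed 50%. For the NRT arm (n=162) it gives 0.077. It then describes about plus or minus 5 percentage points as acceptable.
- The same paragraph illustrates how intervals narrow away from 50%: "95% CI on 90% would range from 0.896 to 0.931 with n=324".
- Section IIIc, Randomization and Stratification, explains the 2:1:1 allocation by the wish to "increase precision of our parameter estimates within the varenicline group (n=324"). Section IIIi, Power, also arrives at 324 varenicline participants. On the total it says "we will enroll between 648-660 participants to abide by those at earlier steps of the process".
- Section II hypothesizes that "use of varenicline will be strong: >80% of study sample using medications" on at least half of the sampling period. The first feasibility criterion in Section IIIi is that "at least 80% of varenicline group tries the medication".
- On pace, Section IIIi, Power, says: "Over a 48-month recruitment span (see Timeline below), we aim to recruit ~11/month".
- Section IIIc, Teleconsent, says that about 55% of mailed consent forms are not returned and concludes that, for a minimum of 648, "we would need to identify ~1180 who would be eligible and interested".

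**The concern.** The paragraph that quantifies Aim 1 precision uses two different sizes for the same arm, and the larger one has no support elsewhere in the plan. The example interval at 90% also looks wrong on its face: it reaches 0.004 below 0.90 but 0.031 above it.

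Aim 1 (uptake, use, conversion) is a primary aim analysed mainly by estimation within each arm. Precision in the varenicline arm is the stated reason for giving that arm half the participants, and this paragraph is where that precision is put into numbers. The use hypothesis and the first feasibility criterion both sit at 80%. The plan's only example in that upper range makes the estimates look about twice as precise as they will be.

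The recruitment pace and the consent yield are separate matters. They bear on feasibility planning, not on inference.

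**Working it through.** **Inputs.** Two-sided 95% intervals; allocation 2:1:1; total 648 to 660; varenicline n=324 (Sections IIIc and IIIi) or 360 (Section IIIi, Aim 1 only); NRT n=162; pace about 11 per month for 48 months; about 55% of mailed consents not returned.

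**Arm size.** Varenicline receives half of the total: 648/2 = 324 and 660/2 = 330 (330 is derived, not printed). An arm of 360 needs 360/0.5 = 720 randomized. The 324 agrees with the plan's own power calculation: 413/0.85 = 486 = 324 + 162.

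**Maximum half-width.** Wald formula, 1.96 × sqrt(0.25/n):

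| n | Half-width at 50% | Interval | Stated |
|---|---|---|---|
| 360 | 0.0516 | 0.448 to 0.552 | 0.052, reproduced |
| 324 | 0.0544 | 0.446 to 0.554 | not given |
| 330 | 0.0539 | 0.446 to 0.554 | not given |
| 162 (NRT) | 0.0770 | 0.423 to 0.577 | 0.077, reproduced |

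The NRT figure confirms that the plan used the Wald formula. The varenicline figure matches the formula at 360, not at 324 or 330.

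**Interval at 90%, n=324.**

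- Wald: 1.96 × sqrt(0.09/324) = 0.0327, so 0.867 to 0.933, width 0.065.
- Wilson: 0.862 to 0.928.
- Exact (Clopper-Pearson): 0.862 to 0.930, width 0.068.

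The Wilson and exact limits use 0.9 × 324 = 291.6 events. With the whole count of 292 they become 0.864 to 0.929 and 0.863 to 0.932 (0.9315 before rounding).

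The printed interval has width 0.931 − 0.896 = 0.035, which is 0.035/0.0653 = 54% of the Wald width and 0.035/0.0684 = 51% of the exact width. A Wald width of 0.035 at 90% would need 0.09 × (1.96/0.0175)² ≈ 1,129 participants.

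A likely origin: Wald at n=360 is 0.869 to 0.931. The printed upper limit matches this, and 0.896 is 0.869 with two digits swapped. That is an inference.

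**Half-width at 80%.** n=324: 1.96 × sqrt(0.16/324) = 0.0436, so 0.756 to 0.844.

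**Pace.** 11 × 48 = 528, which is 120 short of 648 (81% of it). The target needs 648/48 = 13.5 to 660/48 = 13.75 per month. At 11 per month it takes 648/11 = 58.9 to 660/11 = 60 months. Rounding does not explain the gap: 11.49 × 48 = 552.

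**Consent yield.** 648/0.55 = 1,178, which matches the stated figure of about 1180 but treats 55% as the share returned. With 55% not returned, 648/0.45 = 1,440.

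**The case against.** The strongest reply is that this is clerical. One stale calculation at n=360 plus one digit swap would account for both precision errors. On that reading the intended width at 90% was 0.062 against a correct 0.065, so halving describes a misprint and not a belief about precision. The 360-for-324 slip alone moves the half-width by only 0.003 at 50%, and by 0.002 at 80% (0.0413 to 0.0436). The plan accepts roughly 5 points, no decision rule uses a confidence limit, feasibility is expressly not a main outcome, and the reported intervals will come from the data. Other feasibility criteria sit at 50% and 30%, where the example at 90% is not relevant; at 30% with n=324 the half-width is 0.050. Sample size rests on abstinence in Aim 2.

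Most of this stands as a limit on consequence. It does not make the printed figures right: a reader sees 0.896 to 0.931 labelled n=324, and the lower limit is wrong by any method. With 292 events the exact upper limit comes close to the printed one, but the lower limit still fails.

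On recruitment, the plan refers to a Timeline that is not in the text reviewed, and it cites faster accrual in other studies (about 25 per month nationwide, 157 in five months, more than 375 in 15 months). That suggests the target may be reachable, but it does not reconcile the two stated numbers. The figure of about 1180 belongs to the account of mail-only consent and drives no design quantity, so it is an editorial note.

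**Conclusion.** The concern holds. The varenicline arm size of 360 contradicts the 324 given in Sections IIIc and IIIi, including the same paragraph. The correct maximum half-width is 0.054 at either 324 or 330, against 0.052 stated, a small difference. The worked interval at 90% is wrong at n=324: its width should be 0.065 (Wald) to 0.068 (exact), against 0.035 printed. About 11 per month for 48 months yields 528, not 648 to 660.

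These results assume 2:1:1 allocation is achieved and that the full varenicline arm is the denominator. The planned sample size, the 80% power for the primary comparison, the allocation and the analyses are all unaffected, because enrolment is set by number. The figures should be corrected because they are the stated precision for a primary aim and support the stated reason for unequal allocation.

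**What to change.** In Section IIIi, Aim 1 precision:

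1. Replace 360, 0.052 and 0.448 to 0.552 by 324, 0.054 and 0.446 to 0.554.
2. Replace 0.896 to 0.931 by 0.867 to 0.933, and name the method (Wald).
3. Describe the accepted precision at a 50% rate as about plus or minus 5.4 points for varenicline and 7.7 points for NRT.
4. Preferably add the half-width at 80% (0.044, that is 0.756 to 0.844), since the hypothesis and the first feasibility criterion use that value. This is a useful addition, not the correction of an error.

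In Section IIIi, Power, reconcile the pace with the span: either 13.5 to 13.75 per month over 48 months, or about 59 to 60 months at 11 per month.

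In Section IIIc, reconcile the figure of about 1180 with the statement that about 55% of forms are not returned. No replacement is proposed, because either number may be the slip and teleconsent changes the yield.

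The cost is wording only, with no change to sample size, power, allocation or analysis.
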